13.2 Treatment Exposure

Extent of exposure will be calculated in days using the following:

$$\text{Extent of Exposure (days)} = [\text{Date of last dose} - \text{Date of first dose}] + 1$$

Extent of treatment exposure (days) and the total number of doses received for each subject exposed to IMP will be summarized with continuous descriptive statistics using the Safety set. A subject listing of treatment exposure will also be produced.

14. Analysis of the Primary Endpoint

The primary endpoint is the mean change from baseline (Visit 2 / Day 1) to end of treatment (Visit 8 / Day 43) in BCVA letter score of the study eye as measured by the ETDRS testing method using the Evaluable set. BCVA will be measured at the beginning of every study visit and change from baseline for each subject will be calculated as follow-up visit minus baseline visit. Quantitative summary statistics will be used to summarize the BCVA letter score and change from baseline at each visit. A two-tailed, one-sample t-test will be used to assess the mean change from baseline in BVCA letter score at each visit, in which the change from baseline BCVA letter score will be compared to a reference value of zero. The following SAS code will be used to run the one-sample t-test:

```
PROC TTEST H0=0 ALPHA=0.20 DATA=INDATA;
  VAR BCVA_CHG;
RUN;
```

where

- *INDATA* is the name of the input dataset;
- *BCVA_CHG* is the change in BCVA from baseline to the follow-up visit.

A mixed model accounting for repeated measures will also be used to analyze BCVA. This model will include the change from baseline in BCVA letter score as the response variable and baseline BCVA letter score, smoking status and visit as explanatory variables for adjustment. LS means for each visit will be calculated along with corresponding 95% CIs and p-values. SAS code to implement this repeated measures mixed model is as follows:

```
PROC MIXED DATA=INDATA;
  CLASS SUBJID SMOKE VISIT;
  MODEL CHG = BASELINE SMOKE VISIT / DDFM = KR SOLUTION;
  REPEATED VISIT / SUBJECT=SUBJID TYPE=UN;
  LSMEANS VISIT / CL;
RUN;
```

where

- *INDATA* is the name of the input dataset sorted by *SUBJID* and *VISIT*;
- *SUBJID* is the subject ID number;
- *SMOKE* is the subject's smoking history (Never smoked, Ex-smoker, Currently smokes);
- *VISIT* is the visit at which the BCVA letter score was collected;

- *CHG* is the change from baseline in the BCVA letter score;
- *BASELINE* is the baseline BCVA letter score;

The Kenward-Roger method will be used to determine denominator degrees of freedom. An unstructured variance-covariance matrix will be used for the above repeated measures model. If the model does not converge using the unstructured matrix, the first order autoregressive structure and the compound symmetry structure will be employed, in that order.

The above analyses will be repeated on the PP set as a sensitivity analysis.

Additionally, the number of subjects with change from baseline in BCVA letter score for the following categories will be summarized with counts and percentages:

- ≥ 15 letters;
- ≥ 14 and ≥ 10 letters;
- ≥ 9 and ≥ 5 letters;
- ≥ 4 and ≥ -4 letters;
- ≥ -5 and ≥ -9 letters;
- ≥ -10 and ≥ -14 letters;
- ≤ -15 letters.

BCVA results will also be presented in a data listing. BCVA results in the fellow eye are not included in the analyses but will be included in the listings. BCVA will also be summarized by visit using box plots.

15. Analysis of the Secondary Endpoints

The analyses for secondary endpoints (incidence, seriousness and severity of AEs) will be discussed in the next section as part of the safety analyses. There is no secondary efficacy endpoint for the study.

16. Safety Analyses

Safety will be assessed for the following endpoints using the Safety set:

- Incidence, seriousness, and severity of AEs;
- Observed slit-lamp biomicroscopy values;
- Observed intraocular pressure (IOP) values;
- Changes from baseline in clinical laboratory values;
- Changes from baseline in physical examination;
- Changes from baseline in vital signs.

Adverse events will be presented using frequencies and percentages of subjects.

Other safety endpoints including slit-lamp biomicroscopy, IOP, clinical laboratory values, physical examination, and vital signs will be summarized using descriptive statistics. Changes or shifts from baseline will also be summarized where appropriate. Assessments performed by eye (study eye and fellow eye) will be summarized separately. No statistical inferential testing will be performed for safety variables.

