5.3.2 HANDLING OF PARTICPANT WITHDRAWALS OR TERMINATION

Approximately 30 subjects will be enrolled in the study. Subjects will be encouraged to complete the study and all assessments. However, subjects may voluntarily withdraw at any time, and the investigator may discontinue individual subjects from the study at any time. For subjects who withdraw consent from the study, no study procedures will be done thereafter. For those that withdraw from receiving the study agent, follow-up visits and the safety phone follow-up are to occur as per the protocol. Excluding cases of medical emergency, but prior to the discontinuation of a subject from the clinical study for disease worsening, the study investigator should discuss each case of discontinuation with the sponsor and/or the medial monitor.

The subject withdrawal criterion below should be used to assess worsening or disease progression. In such cases, a documented assessment by the principle investigator is required, and subjects with clinically significant disease progression should be considered for withdrawal from the study and subsequent initiation of standard of care:

- A BCVA loss of ≥ 5 letters from baseline
- New macular subretinal hemorrhage
- Investigator discretion based on acute worsening of underlying disease or substantial risk to further participation in the study

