8.3 Evaluable Set

The Evaluable set includes all subjects who complete at least 3 weeks of treatment during the 6-week treatment period.

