8.4 Per Protocol Set

The Per Protocol set is a subset of the Evaluable set, comprised of all subjects who completed the study and have no major protocol violations.

9. General Statistical Considerations

Final data analysis will be performed by SDC after the study is completed and the database has been cleaned and locked. One interim analysis will be performed by SDC when two-thirds of all enrolled subjects have either completed Day 15 (Visit 4) or prematurely exited the study; at this time, a snapshot of the database will be extracted (without formal pre-database-lock data cleaning) for inclusion in the interim analysis. Statistical programming and analyses will be performed using SAS[®] Version 9.4 or higher.

Unless specified otherwise, all ocular assessments and efficacy outcome measures are with respect to the study eye, hereence. Data collected for the fellow eye (non-study eye) will be included in subject listings and may be analyzed.

Study day will be calculated as (Date of Visit) – (Date of Initiation of Investigational Medicinal Product [IMP]) + 1 for visits after initiation of IMP and as (Date of Visit) – (Date of Treatment Initiation) for visits prior to initiation of IMP.

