9.1 Missing or Inconclusive Data Handling

In general there will be no imputation of missing data other than for partial or missing dates. Partial start and end dates for medical history, concomitant medications, and AEs will be imputed as outlined in [Appendix 1](#). Completely missing dates will only be imputed for AEs.

The original dates will be displayed in data listings along with the relative study day for complete dates. imputed dates will be used in derivations only (e.g., to determine treatment-emergence status, etc.).

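### The Evaluable-set mean BCVA change leans toward improvement to the extent that worsened subjects leave early, and no listed summary gives the post-baseline BCVA change of all treated subjects

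*SAP*

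**What the plan says.** - **Primary analysis.** SAP 14 takes the change from Day 1 to Day 43 in "BCVA letter score of the study eye as measured by the ETDRS testing method using the Evaluable set" and applies a one-sample t-test against zero at two-sided alpha 0.20. A repeated-measures model is planned as well.
- **Evaluable set.** SAP 8.3 defines it as "all subjects who complete at least 3 weeks of treatment during the 6-week treatment period".
- **Per Protocol set.** SAP 8.4 makes it a subset of Evaluable, "comprised of all subjects who completed the study and have no major protocol violations". On sensitivity analysis, SAP 14 says: "The above analyses will be repeated on the PP set as a sensitivity analysis".
- **Missing data and windows.** SAP 9.1: "In general there will be no imputation of missing data other than for partial or missing dates". SAP 9.3 maps only Days 40 to 46 to Visit 8.
- **Withdrawal for worsening.** Protocol 5.3.2 lists "A BCVA loss of ≥ 5 letters from baseline" among the signs of progression, requires a documented assessment, and says that "subjects with clinically significant disease progression should be considered for withdrawal from the study and subsequent initiation of standard of care".
- **Visits after stopping.** Protocol 8.2.3 keeps the end-of-treatment procedures for subjects who stop only the study agent. It allows no procedures after withdrawal of consent.
- **Replacement.** SAP 6 allows subjects who discontinue before Day 22 to be replaced.
- **Outputs.** Tables 14.2.1.1 to 14.2.1.3 and Figure 14.2.1 show BCVA or its change on the Evaluable or PP set only. SAP 8 leaves room for other sets but names none for BCVA change.

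**The concern.** The outcome being averaged can itself be the reason a subject leaves the average. There are two routes.

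1. **Stopping before 3 weeks.** The subject is not Evaluable, whatever is measured later. The repeated-measures model is planned on the same set, so it cannot bring the subject back.
2. **Leaving after 3 weeks.** The subject stays Evaluable but may have no Day 43 value for the t-test. An early-termination BCVA taken before Day 40 is not mapped to Visit 8.

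Both routes remove losses rather than gains. With zero as the reference and no comparator, the Evaluable mean alone cannot separate this selection from a drug effect. The only sensitivity set, PP, is more selected, so agreement between the two would not be reassuring. Protocol 2.2 says that a favourable BCVA effect could be the basis for a longer-term evaluation, so the direction of the error matters.

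**Working it through.** **The plan's own figures.** The plan gives no power, effect size, SD or dropout rate to reproduce. It gives 30 enrolled for about 25 evaluable, an implied loss of 5/30 = 16.7%.

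**Simple identity.** If the 25 Evaluable subjects average m letters and the 5 others lost L letters on average, the mean of all treated is (25m − 5L)/30. With m = 0:
- L = 5: −25/30 = −0.83
- L = 10: −50/30 = −1.67

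This illustrates scale only. The documents do not say that the 5 would be subjects who worsened.

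**Simulation, t-test.** All inputs except n, the visit days, the 5-letter criterion, the 3-week rule and alpha are assumptions.
- n = 30, no replacement, true mean change 0.
- SD of true 6-week change 4 to 8 letters; single-test error SD 2.5 to 3.5; linear course.
- Observed change = true change + visit error − baseline error, rounded to whole letters.
- 25% or 50% of subjects with an observed loss of 5 or more letters at Visits 3 to 7 stop at the first such visit (2.6 to 3.7, or 5.2 to 7.4, of 30). Stops at Day 8 or Day 15 are not Evaluable.
- P(gain) is the chance of a significant improvement; nominal 10%.

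| After stopping | 25%: bias, P(gain) | 50%: bias, P(gain) |
|---|---|---|
| All leave completely | +0.4 to +0.9, 19–22% | +0.9 to +2.0, 33–42% |
| Half of those past 3 weeks keep Day 43 | +0.3 to +0.7, 16–19% | +0.7 to +1.6, 26–33% |
| All of those past 3 weeks keep Day 43 | +0.2 to +0.5, 14–17% | +0.4 to +1.2, 19–26% |
| Complete exit, but only if the true loss is also 5 or more | +0.1 to +0.6 | +0.2 to +1.2 |

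The last row represents an assessment that screens out pure test error. With no withdrawals the bias is nil and P(gain) is about 10%.

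**Other assumptions.** A random-walk course with SD of change 6 to 10 letters and complete exit gives +0.8 to +1.9 at 25% and +1.5 to +3.6 at 50%, so the table is not an upper bound. At a true mean of −1.15 letters (the 10 letters per year of Protocol 2.2 × 6/52), with the assumptions of the table's first row, P(gain) is 1–3% without withdrawals, 2–8% at 25% and 8–21% at 50%.

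**Repeated-measures model, unstructured covariance.** Each cell gives the bias at 25% / 50% with complete exit.

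| Exit depends on | Evaluable set (as planned) | All treated subjects |
|---|---|---|
| Recorded BCVA only (linear, early-change and random-walk courses) | +0.21 to +0.76 / +0.44 to +1.68 | within 0.01 / within 0.01 |
| Recorded and true loss of 5 or more (linear course) | +0.03 to +0.22 / +0.06 to +0.45 | about 0 to +0.15 / +0.05 to +0.35 |

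The value within 0.01 holds by construction, because exit there depends only on data the model sees. In the second row the two sets differ little. With an early course the gap widens: at 25%, up to 0.50 (Evaluable) against 0.15 (all treated).

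**The case against.** **Withdrawal is neither automatic nor always complete.** This stands. A reader might infer that everyone who loses 5 letters drops out of the analysis. The documents do not support that: Protocol 5.3.2 asks for an assessment and only for consideration of withdrawal, and Protocol 8.2.3 keeps end-of-treatment procedures for those who stop only the agent. A flat share of all readings at −5 or worse therefore probably overstates the effect, which is why the screened row is given. The early-exit route remains even if every later Day 43 visit is kept.

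**Worsening is visible elsewhere.** This stands in part. A reader might infer that no summary covers BCVA in all subjects, or that these exits are hidden. Neither is so:
- Baseline BCVA is in the ITT demography table, and losses of more than 15 letters are counted as AESIs on the Safety set (Table 14.3.5).
- Protocol 7.2.1.2.5 records worsening of the underlying disease as an AE, so such exits can appear in Table 14.3.6.1 and Listing 16.2.7.4. Protocol 7.2.1.2.1 is more restrictive about progression, so capture is not assured, and SAP 10 has no separate reason for disease worsening.
- Listings 16.2.3.2 and 16.2.6.1 show who was excluded and every BCVA value.

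With about 30 subjects a reader could compute an observed all-treated mean from the listings. That would be a post hoc calculation in an open-label study, and none of these outputs gives the mean change itself.

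**Other wAMD therapy is prohibited on study** (Protocol 6.4) and prohibited medication is a reason for withdrawal (Protocol 5.3.1). This narrows the question of BCVA measured after standard of care begins, but does not settle it.

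**The study is exploratory.** This stands and limits the severity. SAP 6 says it is not powered, Protocol 10.4.1 that it is not designed to detect significant BCVA change, and no decision depends on the p-value.

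**Conclusion.** The point holds in conditional form. The direction follows from the documents: to the extent that subjects stop for worsening before 3 weeks, or leave without a Day 43 value, the Evaluable mean is too favourable, and no planned summary of post-baseline BCVA change shows by how much.

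The size does not follow from the documents. Under the stated assumptions it runs from about +0.1 letters (25% withdrawn, test error screened out) to about +2.0 (50%, complete exit); with no such withdrawals it is zero. Only the direction should be treated as established.

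Two stronger conclusions are not supported. One is that the trial is likely to report a false gain: at the untreated rate in Protocol 2.2 and 25% withdrawal, that chance stays below the nominal 10%. The other is that a model on all treated subjects removes the bias: it does so only if withdrawal depends on recorded BCVA, whereas Protocol 5.3.2 also lists new hemorrhage and investigator discretion. The consequence is modest, but the correction is cheap and worth making before the data are analysed.

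**What to change.** In SAP 8, 14 and 24, keep the Evaluable t-test as primary and:

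1. Add one prespecified sensitivity table of BCVA change from baseline by visit for all treated subjects with a baseline and at least one post-baseline value, including subjects who were replaced. Fit the planned repeated-measures model to that set.
2. State that this model removes the bias only if withdrawal depends on recorded BCVA, which the data cannot confirm.
3. State whether BCVA measured after the start of other wAMD therapy is used.
4. Report by visit how many subjects withdrew for disease worsening, and how many of them have a Day 43 value.

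The fallback covariance and the weighting of smoking groups in the model are separate, optional choices. No change to the withdrawal criterion is proposed.

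**Cost:** SAP wording, one more model run and one table. The added estimate will probably be less favourable than the primary one.

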8.2.3 END OF TREATMENT

All end of treatment (EOT) study-related procedures will be conducted at the conclusion of 6 weeks of treatment on Day 43 \pm 1. However, for subjects who withdraw consent from the study, no study procedures will be done thereafter. For subjects that withdraw from the study agent, EOT procedures and follow up visits are to occur as per the protocol. Excluding cases of medical emergency, but prior to the discontinuation of a subject from the clinical study for disease worsening, the study investigator should discuss each case of discontinuation with the sponsor.

8.2.3.1 Visit 8

At Visit 8, the following procedures and assessments are performed:

- Pharmacokinetic and biomarker samples are taken
- All ophthalmological assessments: BCVA, SD-OCT, fundus photography/FA, slit lamp, and IOP
- Vital signs, physical examination, safety laboratory tests, **Poland only:** serum pregnancy test (in women of childbearing potential), and 12-lead ECG
- Review of concomitant medications
- AE reporting and evaluation

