10.4 PLANNED ANALYSES

10.4.1 ANALYSIS OF THE PRIMARY ENDPOINT

The therapeutic effect of the treatment will be investigated in one single group of subjects, with no control group. The changes from baseline in BCVA will be compared with 0 as reference value. The study is not designed to detect significant changes in BCVA over time. However, using available data, including changes in BCVA from baseline, descriptive summarization will be developed. Of particular interest will be the within-subject changes in BCVA from baseline and their distribution around a null value of zero.

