3.4 Statistical Hypotheses

The null and alternative hypotheses for change from baseline in BCVA letter score as measured by ETDRS testing method are as follows:

H₀: Mean change from baseline in BCVA letter score at 6 weeks = 0

H₁: Mean change from baseline in BCVA letter score at 6 weeks ≠ 0

The hypothesis testing will be at a two-sided Type I error rate (α) of 0.20. Specifics of the statistical tests are provided in Section 14.

4. Study Design and Procedures

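### In the single-arm repeated-measures model, the default LS means weight the smoking groups equally, so they estimate an equal-groups average and not the mean change of the subjects analysed (minor)

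*SAP*

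**What the plan says.** SAP 14 sets the primary endpoint as the change in study-eye BCVA from baseline to Visit 8 in the Evaluable set, and tests it against zero with a one-sample t-test. It then adds a repeated-measures model. SMOKE, VISIT and SUBJID are class variables, and the model line is "MODEL CHG = BASELINE SMOKE VISIT / DDFM = KR SOLUTION". SMOKE is the subject's "smoking history (Never smoked, Ex-smoker, Currently smokes"). There is no SMOKE-by-VISIT term.

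The visit means come from "LSMEANS VISIT / CL", which carries no weighting option. They are reported in their own right: "LS means for each visit will be calculated along with corresponding 95% CIs and p-values". The analyses then extend to the Per Protocol set: "The above analyses will be repeated on the PP set as a sensitivity analysis". SAP 17.1 has the quantitative imaging endpoints analysed similarly to the primary endpoint.

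The null hypothesis in SAP 3.4 reads "Mean change from baseline in BCVA letter score at 6 weeks = 0". Protocol 10.4.1 states the design: "The therapeutic effect of the treatment will be investigated in one single group of subjects, with no control group". I found no sentence in either document that sets a weighting over smoking groups or says that equal weighting is intended.

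**The concern.** In a two-arm trial with a main-effects model, the weighting over a covariate's levels drops out of the treatment difference. Here the LS mean is itself the estimate and is compared with zero, so the weights stay in it. If few subjects are current smokers, those few receive as much weight as each larger group.

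This matters because of the model's role in the Evaluable set. SAP 9.1 imputes no outcome data, so the Visit 8 t-test omits Evaluable subjects with no Visit 8 value. Stopping study agent does not by itself create such a gap: "For subjects that withdraw from the study agent, EOT procedures and follow up visits are to occur as per the protocol" (Protocol 8.2.3). Leaving the study or missing the visit does. Protocol 5.3.2 has subjects with clinically significant progression considered for withdrawal from the study, so the gaps may be informative. The repeated-measures model is the only planned Visit 8 estimate that uses these subjects' earlier values. A reader who sees it differ from the t-test will want to ask whether missing data explain the gap, and the weighting adds a second, unrelated reason. The coefficients requested by the SOLUTION option would show part of the offset, but SAP 11.1 and 11.2 do not name smoking status among the variables to be summarised.

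**Working it through.** **Inputs.** From the documents: about 25 evaluable subjects (SAP 6), three smoking levels and the model terms (SAP 14). The documents give no smoking mix, smoking effect or SD, and no figure on this point to reproduce. All splits, effects and SDs below are assumptions. Equal weighting as the default is a property of the software.

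**1. Weights.** With s_k the effect of smoking level k:

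LS mean at visit v = intercept + b × mean(BASELINE) + visit_v + Σ w_k s_k

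The default has w_k = 1/3. The subjects' own mean has w_k = p_k, their share. So

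shift = Σ (1/3 − p_k) s_k

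If only current smokers differ, by d letters, then shift = (1/3 − n_current/25) × d:

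| never/ex/current | calculation | shift |
|---|---|---|
| 9/8/8 | 1/3 − 8/25 | 0.013 d |
| 10/10/5 | 1/3 − 5/25 | 0.133 d |
| 12/10/3 | 1/3 − 3/25 | 0.213 d |

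Because there is no SMOKE-by-VISIT term, with complete data d is the smoking difference averaged over visits, not the Visit 8 difference.

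One simulated complete dataset (12/10/3) confirmed the identity. The raw Visit 8 mean was -1.24, the observed-margin LS mean -1.24 and the default LS mean -1.96. The gap of -0.72 is what the formula predicts.

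**2. Example at 12/10/3.**
- Gap of -3 at every visit, others 0: trial mean = -3 × 3/25 = -0.36; LS mean = -3 × 1/3 = -1.00.
- Gap growing linearly to -3 over the six visits from Visit 3 to Visit 8: average gap = -3 × 3.5/6 = -1.75; shift = 0.213 × (-1.75) = -0.37; LS mean = -0.36 − 0.37 = -0.73.

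For scale only, the protocol's untreated loss of 10 letters a year (Protocol 2.2) is 10 × 6/52 = 1.15 letters over six weeks if linear. This does not bound d.

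**3. Precision.** I used generalised least squares with visit and SMOKE effects, n = 25, 6 or 8 visits, compound symmetry or AR(1), and correlation 0.5 to 0.9. BASELINE and the planned unstructured matrix were left out. With complete data the Visit 8 SE, relative to a model without SMOKE, is

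ratio = √[1 + f × (25 × Σ 1/(9 n_k) − 1)]

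Here f is the variance of the estimated all-visit mean relative to that of one visit. Its largest value is (1 + 5 × 0.9)/6 = 0.917 (compound symmetry, 6 visits). Its smallest is 1.5/(8 − 6 × 0.5) = 0.30 (AR(1), 8 visits).

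At 12/10/3, 25 × (1/12 + 1/10 + 1/3)/9 = 1.435, so the ratio runs from √(1 + 0.30 × 0.435) = 1.063 to √(1 + 0.917 × 0.435) = 1.183.

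| split | SE ratio, default | SE ratio, subject-level margins |
|---|---|---|
| 9/8/8 | 1.000–1.001 | 1.000–1.001 |
| 10/10/5 | 1.017–1.050 | 1.000–1.001 |
| 12/10/3 | 1.063–1.183 | 1.000–1.001 |

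If one subject per smoking level has no data after Visit 5, the default ratio at 12/10/3 is 1.082–1.182.

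With an assumed SD of 10 letters, the 95% half-width without SMOKE is 2.064 × 10/5 = 4.13 letters. The loss at 12/10/3 is 4.13 × 0.063 = 0.26 to 4.13 × 0.183 = 0.76 letters.

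**4. Rejection rate, illustrative.** Take a true trial mean of 0, 12/10/3, SD 8 to 12, a gap constant over visits and a two-sided 0.20 level. Then P(|Z + shift/SE| > 1.2816), with SE = (SD/5) × 1.063 to 1.183, is 20.1–20.4% for d = 1, 20.2–20.5% for d = 1.15 and 21–23% for d = 3.

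**The case against.** The strongest reply is that this is a preference. The model is additional to the t-test, balanced margins are the ordinary default for an adjusted mean, and the SAP never promises that this mean equals the raw one. Raw means and t-tests are reported at every visit. The two estimates would differ anyway, because the model uses data from subjects who leave early. The study is exploratory and unpowered (SAP 6 and 9.5), and no decision rule uses the LS mean. All of this stands and keeps the point minor. It does not settle what the LS mean estimates: SAP 14 ties the analysis to the Evaluable and PP sets, and nothing says that an equal-groups average was wanted.

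A reader might infer more than the documents support:

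- *That the code contradicts the null hypothesis.* SAP 3.4 names no analysis set, so the mismatch is with the sets named in SAP 14. The t-test of that hypothesis is untouched.
- *That the 0.20 error rate of the trial's test is inflated.* SAP 9.4 assigns 0.20 to the primary efficacy analysis, and SAP 14 codes it only in the t-test. The model has 95% intervals. The rejection rates above are illustrations.
- *That the missing-data argument carries to the PP repeat.* SAP 8.4 limits that set to completers, so little dropout remains there. Only the weighting itself carries over.
- *That the estimate must be shifted.* The groups have to differ both in size and in mean change. Without a smoking effect, an uneven mix costs only precision.

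**Conclusion.** The point holds for the code as written, and it is minor. The supplementary LS means target an average over equal smoking groups, and in a single-arm comparison with zero this cannot cancel. The size depends on quantities that the documents do not give. With groups near equal it is nil. At an assumed 12/10/3 split, the Visit 8 SE rises by 6 to 18%. A 3-letter deficit in current smokers moves the estimate by 0.64 letters if constant over visits, or by 0.37 if it grows linearly to Visit 8. One-third weights require all three levels in the data; with one empty, the other two get one half each. The effect on the imaging endpoints depends on whether they are analysed with this model, which SAP 17.1 leaves open.

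**What to change.** Keep SMOKE and the model, and change the request to `LSMEANS VISIT / CL OM=dataset`. The margin dataset should hold one row per subject of the analysis set at each visit level in the model, with SMOKE and BASELINE, so that the margins follow the subjects' smoking distribution.

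Plain OM is not a safe substitute. If the input data have no rows for missed visits, it down-weights subjects who leave. In the constant-gap example, suppose the 3 current smokers leave after Visit 5 (3 visits each) and the other 22 complete all six. The current smokers' weight becomes 3 × 3/(3 × 3 + 22 × 6) = 9/141 = 6.4% instead of 12%, and their contribution is -3 × 0.064 = -0.19 instead of -0.36.

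State the weighting in one sentence of SAP 14. Apply it to the PP repeat and to any quantitative SD-OCT endpoint analysed with this model under SAP 17.1. If equal weighting is in fact wanted, that sentence should say so.

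The cost is one margin dataset per analysis set, one line of code and one sentence. The covariates and the t-test stay as planned.

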7. End of Treatment (EOT) visit (Visit 8): all study related procedures will be conducted at the conclusion of 6 weeks of treatment on Day 43 ±1. Withdrawal of consent is allowed at any time. For subjects who withdraw consent from the study, no study procedures will be done thereafter. For those that withdraw from the study agent, follow-up visits are to occur as per the protocol. Excluding cases of medical emergency, but prior to the discontinuation of a subject from the clinical study for disease worsening, the study investigator should discuss each case of discontinuation with the sponsor.
8. Adverse events and concomitant medications will be assessed at every study visit as well as recorded at any unscheduled subject contact (e.g., unscheduled phone calls, etc.). Following completion of study agent treatment (Visits 2-8), all current medications will be assessed in the follow-up period.
9. Pregnancy test required in Poland only per Inclusion Criteria.

5. Study Treatments

This is a single arm, open-label study. All subjects will receive the investigational treatment ALK4290 at a daily dosage of 800 mg administered orally twice a day as 400 mg tablets for 6 weeks.

6. Sample Size and Power Considerations

A total of 30 subjects will be enrolled in the study with the intent of obtaining approximately 25 evaluable subjects who would complete at least 3 weeks of treatment and evaluations through Visit 5 (Day 22). Subjects who discontinue prior to Day 22 may be replaced. Subjects who withdraw or are withdrawn during screening (prior to completing V2) will be replaced. The study is not powered for detecting statistically significant differences in therapeutic parameters in subjects with wAMD receiving ALK4290.

7. Data Preparation

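### If the unstructured covariance in the supplementary BCVA mixed model fails to converge, the only fallbacks force equal variance at all visits, which can understate the Visit 8 standard error; add heterogeneous structures first

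*SAP*

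**What the plan says.** SAP section 14 puts a t-test first for the primary endpoint: "A two-tailed, one-sample t-test will be used to assess the mean change from baseline" at each visit, with Visit 8 as the primary time point in the Evaluable set. A mixed model is then added, with baseline BCVA, smoking status and visit as explanatory variables and Kenward-Roger degrees of freedom. Its covariance is coded as "REPEATED VISIT / SUBJECT=SUBJID TYPE=UN", and the text confirms this: "An unstructured variance-covariance matrix will be used for the above repeated measures model".

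The contingency reads "If the model does not converge using the unstructured matrix", then "the first order autoregressive structure and the compound symmetry structure will be employed, in that order". Section 14 names no structure with visit-specific variances other than the unstructured one, and no robust standard error.

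On output, "LS means for each visit will be calculated along with corresponding 95% CIs and p-values". On data, "BCVA will be measured at the beginning of every study visit", and the schedule in SAP section 4.2 places visual acuity at Visits 3 to 10 after baseline. The SAP does not say which of these visits enter the model. SAP section 6 gives the size: "A total of 30 subjects will be enrolled in the study with the intent of obtaining approximately 25 evaluable subjects".

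**The concern.** An unstructured matrix over eight visits is large for about 25 subjects, so the contingency could be needed. AR(1) and CS, as named, estimate a single variance and apply it at every visit. Day 8 is one week after baseline and Day 43 is six weeks after, so change scores could plausibly be more spread out at Day 43. If so, the early visits pull the common variance below the true Visit 8 variance. The model's Visit 8 standard error, interval and p-value would then look more precise than they are. Kenward-Roger adjusts for estimating the covariance parameters; it does not repair a wrong variance structure.

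What is at stake is the adjusted analysis, not the t-test. BCVA is not imputed (SAP section 9.1), and Protocol section 5.3.2 has subjects with disease worsening considered for withdrawal. A subject without a Visit 8 value drops out of the Visit 8 t-test, whereas the mixed model still uses that subject's earlier visits. The model therefore matters most when dropout is high, which is also when the unstructured fit is most likely to fail.

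**Working it through.** The documents state no SD for BCVA change, no correlation and no parameter count, so there is no plan figure to reproduce. The SD profiles, correlations and dropout rates below are assumptions.

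**1. Parameter counts**, for k post-baseline visits:

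| Structure | Formula | k = 8 (Visits 3-10) | k = 6 (Visits 3-8) |
|---|---|---|---|
| Unstructured | k(k+1)/2 | 36 | 21 |
| TOEPH | 2k-1 | 15 | 11 |
| ARH(1) or CSH | k+1 | 9 | 7 |
| AR(1) or CS | 2 | 2 | 2 |

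**2. How often the unstructured fit fails.** Two sets of proxy fits were run, neither of them in PROC MIXED, with 60 simulated datasets per setting.
- Maximum likelihood, means only: at 25 subjects, 0 of 60 failed in every setting (6 or 8 visits, 15% or 40% dropout). At 20 subjects, 8 visits and 40% dropout, about 10% failed; the other settings at 20 subjects had no failures.
- REML with baseline and three-level smoking, 8 visits: at 25 subjects, 0, 1 and 8 of 60 failed with dropout of 0%, 20% and 40%. At 20 subjects and 40% dropout, 27 of 60 failed.

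**3. Size of the effect once the fallback is used.** With complete data, the CS variance is the mean of the visit variances. The Visit 8 standard error ratio is then sqrt(mean of SD²) / SD at Visit 8. Let the SD rise linearly from Visit 3 to Visit 8 and stay flat at Visits 9 and 10:
- 4 to 10: SDs 4, 5.2, 6.4, 7.6, 8.8, 10, 10, 10. Mean square = 519.2/8 = 64.9; root = 8.06; ratio = 8.06/10 = 0.81.
- 5 to 9: mean square = 467.2/8 = 58.4; root = 7.64; ratio = 7.64/9 = 0.85.
- 6 to 8: mean square = 424.8/8 = 53.1; root = 7.29; ratio = 7.29/8 = 0.91.

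The large-sample AR(1) fit, with true correlation 0.8 to the power of the visit lag, gives 0.79, 0.84 and 0.90.

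Approximate type I error at a nominal 0.20 is 2 × (1 − Φ(1.2816 × ratio)). Approximate 95% coverage uses t with 24 df.

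| SD, Visit 3 to Visit 8 | SE ratio | Type I error | 95% coverage |
|---|---|---|---|
| 4 to 10 | 0.79-0.81 | 0.30-0.31 | about 89% |
| 5 to 9 | 0.84-0.85 | about 0.28 | 90-91% |
| 6 to 8 | 0.90-0.91 | 0.24-0.25 | about 93% |
| flat | 1.00 | 0.20 | 95% |

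A simulation of 1,500 trials of the 4-to-10 case with 25 subjects gave AR(1) rejection 0.32, CS rejection 0.31 and AR(1) coverage of about 88%. A further 3,000 simulated trials per profile gave AR(1) rejection of 0.33, 0.28 and 0.24 for the three rising profiles and 0.21 for the flat one.

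**4. Other shapes, eight visits.** If the SD rises to Visit 8 and faster afterwards (4 to 9, then 11 and 13), the ratio is 0.93-1.01. If it falls linearly from 10 to 6 over Visits 3 to 10, the ratio is about 1.14, so the interval is too wide.

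**5. A heterogeneous fallback.** ARH(1) in the 4-to-10 case gave a standard error ratio of 0.99 and coverage of 94.5%.

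**The case against.** A reader might infer that 36 parameters on 25 subjects will force the fallback. The documents do not support that. The unstructured matrix is the stated default, it estimates the Visit 8 variance freely, and it was usually estimable in the proxy fits at the planned size. The Evaluable set requires at least three weeks of treatment, and Protocol section 8.2.3 keeps subjects who stop the agent in the visit schedule; both limit missing data.

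A reader might also infer that AR(1) and CS always make the Visit 8 interval too narrow. They do so only if the Visit 8 variance exceeds the pooled variance, and no SD in either document shows that it will. The 4-to-10 profile is strong growth: the variance rises 100/16 = 6.25-fold in five weeks.

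The 0.32 is also conditional on fallback. With failure in 8 of 60 fits (13%), and assuming that failure is unrelated to the test result, the overall rate is about 0.20 + 0.13 × (0.32 − 0.20) = 0.22. Finally, the trial is not powered, and the t-test uses Visit 8's own SD.

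All of this stands, and it makes the severity low. It does not remove the gap. The SAP names no heterogeneous fallback, and failure becomes more likely with heavy dropout or fewer subjects. The Per Protocol repeat can be no larger than the Evaluable set, although its restriction to completers limits missing values. SAP section 17.1 analyses quantitative exploratory endpoints in a manner similar to the primary. For PED, height is collected only when a detachment is present, so the usable number may be smaller.

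**Conclusion.** The point holds in conditional form, as a low-severity and cheap improvement. Two things must both happen: the unstructured model fails, and the spread of BCVA change grows with time. The mixed model's Visit 8 standard error is then too small by about 10% (SD 6 to 8), 15-16% (5 to 9) or 19-21% (4 to 10). Given fallback, type I error is about 0.24 to 0.32 against 0.20, and 95% coverage is about 88-93%. These figures assume eight visits, complete data, correlation 0.8 to the power of the lag, and SDs that are not in the documents. A flat SD gives no effect, and a falling SD errs in the other direction.

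It would be wrong to conclude that the primary result is at risk: the one-sample t-test does not depend on this covariance choice.

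**What to change.** In the covariance paragraph of SAP section 14, put heterogeneous-variance structures ahead of AR(1) and CS: for example TOEPH, then ARH(1), then CSH, with AR(1) and CS kept as last resorts. In the same sentence, state which visits enter the model.

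The cost is one sentence and a change of the TYPE= option, a few more variance parameters (9 for ARH(1) or CSH over eight visits, against 2) and, where spread grows, slightly wider intervals. A wrong correlation pattern could still leave some error.

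Dropping Visits 9 and 10 should not be required. It would cut the unstructured matrix to 21 parameters, but it would lose the follow-up LS means. It would also make the existing fallback worse: in the 4-to-10 case the CS ratio becomes sqrt(319.2/6)/10 = 0.73 (AR(1) 0.74), against 0.79-0.81 with eight visits.
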